  - Incidence rate of adverse events regarding electrocardiogram (ECG) findings indicative of QT interval prolongation, according to the physician's information
- For objective **II.h**:
  - Frequency of use of DXA scans in defined time periods:
    - Among patients with >1-year treatment, the number and proportion of Yselyt® users who received at least 1 DXA scan between 10 months until 14 months
    - Among patients with >2-year treatment, the number and proportion of Yselyt® users who received at least 2 DXA scans between 10 months until 26 months
    - Among patients with >3-year treatment, the number and proportion of Yselyt® users who received at least 3 DXA scans between 10 months until 38 months
    - Among patients with ≥4-year treatment, the number and proportion of Yselyt® users who received at least 4 DXA scans between 10 months until end of study
  - Frequency of DXA scans prior to treatment initiation in patients at high risk for osteoporosis or bone loss

---

 Additional analyses on ADRs will be performed.

 The RMP (see 15.1) contains targeted follow-up questionnaires for these events. Physicians who report these events will be asked to fill the corresponding targeted follow-up questionnaire.

 The RMP (see 15.1) contains targeted follow-up questionnaires for these events. Physicians who report these events will be asked to fill the corresponding targeted follow-up questionnaire.

 High risk patients will be identified by their treating physician as described in section 9.2.1.

- Number and proportion of patients who received Yselty® at a dose of 200 mg for more than 6 months without concomitant prescriptions for ABT at suitable time periods (e.g., 3-month intervals)
- For objective **II.i**:
  - Incidence rate of ADRs
  - Incidence rate of SADR
- For objective **II.j**:
  - Mean absolute and relative change in density (g/cm^2) and absolute value and relative change of BMD z-score and t-score from baseline (for patients with baseline DXA scan as per routine clinical practice – per SmPC only recommended for patients at high risk for osteoporosis or bone loss)

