**Table 1 Estimated schedule for the Yselty® PASS**

	First Visit (Enrolment)	Baseline (Yselty® Treatment Start) 	Observation Time Points  (Months Since Yselty® Treatment Start)			
			12	24	36	48
Assessment of inclusion/exclusion criteria	X	–	–	–	–	–
Date of signed informed consent	X	–	–	–	–	–
Date of first Yselty® dose	–	X	–	–	–	–
Year of birth	X	–	–	–	–	–
Sex	X	–	–	–	–	–
Height/weight	X	–	–	–	–	–
Yselty® dosing regimen (100 mg without ABT, 100 mg with ABT, or 200 mg with ABT)	X	–	X	X	X	X
Medical history	X	–	–	–	–	–
Concomitant diseases	X	X				
Alcohol/nicotine/drug/stimulant consumption	X	–	X	X	X	X
Relevant prior medication	X	–	–	–	–	–
Relevant concomitant medication	X	–	X	X	X	X
BMD assessment, including absolute density values, z-score/t-score values, DXA scan date, anatomic site of DXA scan, machine type, imaging parameters, reference population used (if available)	X	–	X	X	X	X
Clinical evaluation (including weight, blood pressure, clinical assessment of fibroid)	X	–	X	X	X	X
Change in Yselty® dosing regimen, reasons for change	–	–	X	X	X	X
Reported adherence to prescribed treatment	–	–	X	X	X	X
Laboratory values  and date of laboratory assessment (if available)	X	–	X	X	X	X
Liver enzyme elevation events 	X	–	X	X	X	X
Bone fracture events 	X	–	X	X	X	X
Events of uterine endometrial adenocarcinoma and mammary gland adenocarcinoma	X	–	X	X	X	X

	First Visit (Enrolment)	Baseline (Yselty® Treatment Start) 	Observation Time Points  (Months Since Yselty® Treatment Start)			
			12	24	36	48
Mood disorder events 	X	–	X	X	X	X
Cardiac disorder events suggestive of potential QT interval prolongation	X	–	X	X	X	X
ECG findings indicative of QT interval prolongation, according to the physician's information	X	–	X	X	X	X
RMP targeted follow-up questionnaires on uterine endometrial and mammary gland adenocarcinoma, QT interval prolongation, exposure in pregnancy/pregnancy outcome, cases of elevated liver enzymes 			X	X	X	X
AEs, SAEs, ADRs, SADRs, special situations 	X	–	X	X	X	X
Premature discontinuation, including reasons 	–	–	X	X	X	X

1 Date of first visit (enrolment) and date of first Yselty® dose (baseline) may be the same, or the date of first Yselty® dose may be up to 3 months prior to first visit. For patients with first Yselty® treatment before enrolment, baseline data can be documented retrospectively at enrolment.

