### **9.3.4 Exposure/Treatment**

Information to be documented on Yselty® exposure/treatment includes:

- Start date
- Stop date (if applicable)
- Dosing regimen (200 mg with ABT, 200 mg without ABT, 100 mg with ABT, 100 mg without ABT)

---

 Exposure/treatment variables will inform on the exploratory endpoint assessing the proportion of patients starting each Yselty® dosing regimen, time spent on each dosing regimen, and changes in dosing regimens.

- Reason for interruption or premature discontinuation of Yselty® treatment (AE, withdrawal of consent, lost to follow-up, treatment with Yselty® discontinued permanently [pregnancy, onset of menopause], administrative problems, death, other), if applicable
- Reason for interruption or premature discontinuation of ABT (AE, withdrawal of consent, lost to follow-up, treatment with ABT discontinued permanently, administrative problems, death, other), if applicable
- Reason for dosing regimen change, if applicable

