### **9.3.6 Variables to Assess the Exploratory Endpoints**

The variables for the exploratory endpoints are:

- For objective **II.a**:
  - Osteoporosis diagnoses
  - Bone fracture events (long bones, spine)
  - For fractures, the probability of an osteoporotic cause of the fracture judged by the physician
  - Laboratory values of 25-hydroxy vitamin D, if available
- For objective **II.b**:
  - Laboratory values of liver enzyme levels or values indicative of liver injury such as alanine aminotransferase (ALT), aspartate aminotransferase (AST), bilirubin, gamma-glutamyl transferase (GGT), and alkaline phosphatase (ALP), if available
  - Date of laboratory assessment of liver enzyme levels, if performed
  - Elevated liver enzyme events
  - Events indicative of liver injury
- For objective **II.c**:
  - Mood disorder events of mood swings, affect lability, emotional disorder, irritability, mood altered, anxiety, bipolar disorder, mania, depression, depressed mood

- For objective **II.d**:
  - Uterine endometrial adenocarcinoma events
  - Mammary gland adenocarcinoma events
- For objective **II.e**:
  - Yselty® dosing regimen and changes in dosing regimens (see section 9.3.4)
- For objective **II.f**:
  - Reported patient adherence to prescribed treatment, including use of ABT
- For objective **II.g**:
  - Cardiac disorder events (ventricular arrhythmias [e.g., ventricular tachycardia and ventricular fibrillation, flutter, torsade de points], cardiac arrest, and sudden cardiac death) suggestive of potential QT interval prolongation
  - ECG findings indicative of QT interval prolongation, according to the physician's information
- For objective **II.h**:
  - DXA scan in defined time periods; Yes/No (see section 9.1.2)
  - DXA scan prior to treatment initiation in patients with risk factors for fractures, osteoporosis, or bone loss; Yes/No
  - Prescription of 200 mg Yselty® without concomitant ABT in defined time periods; Yes/No (see section 9.1.2)
- For objective **II.i**:
  - ADRs
  - SADR
- For objective **II.j**:
 

For patients with multiple DXA scans (at baseline and/or follow-up[s]):

  - BMD z-score and BMD t-score measured in lumbar spine, total hip, or femoral neck
  - Absolute value of density (g/cm^2)
  - Date of DXA scan, if performed
  - Anatomic site of DXA scan, machine type, imaging parameters of DXA scan, and reference population used, if available

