Summary statistics for the treatment duration will be provided. The dosing regimen patterns and reasons for dosing regimen switch will be evaluated by descriptive statistics. Summary statistics will be provided for incidences and reasons for dosing regimen interruption or premature discontinuation of Yselyt® and/or ABT. A transition table will be provided to compare prescribed baseline regimens with prescribed end of study regimens.

For reported adherence to the prescribed treatment, documented deviations from the prescribed dosing regimen will be evaluated by descriptive statistics.

For rates of AEs regarding cardiac disorders (ventricular arrhythmias [e.g., ventricular tachycardia and ventricular fibrillation], cardiac arrest, and sudden cardiac death) indicative of potential QT prolongation, the number and percentage of patients with these events and total number of events as well as the EAIR will be provided including 95% CIs. Events indicative of potential QT interval prolongation will be specified in the SAP based on the MedDRA coding system version available at the time of statistical analysis. Number and percentage of patients with QT interval prolongation as reported by physicians following ECG measurement will be evaluated by descriptive statistics. The incidence rates, as well

---

Additional analyses on ADRs will be performed. Considered as special situations in this study. See definition at end of this section.

as the number and percentage of patients, are also presented for the subgroup of patients in whom the AEs were categorised as ADRs.

Frequency of DXA scans in defined time periods (see section 9.1.2) and frequency of DXA scans prior to treatment initiation in patients with risk factors for osteoporosis and bone loss will be evaluated by descriptive statistics. The results will also be displayed stratified by dose (100mg/100mg + ABT/200mg + ABT)

Number and percentage of patients with an initial treatment dose of 200 mg without ABT that are not treated with ABT after  $\geq 6$  months,  $\geq 9$  months,  $\geq 12$  months,  $\geq 15$  months (continuing at 3-month intervals) while continuing a 200 mg dose of Yselty® will be evaluated by descriptive statistics.

For ADRs and SADR, the incidence as well as EAIR, will be provided including 95% CIs on MedDRA system organ class (SOC) and preferred term (PT) level.

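### The planned count of prolonged 200 mg use without add-back therapy is limited to patients who started on that regimen, while endpoint II.h has no such limit

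*Protocol*

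**What the plan says.** Objective II.h asks, among other things, whether prescribers respect the restriction on 200 mg without ABT. The protocol describes this check in three places.

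- **Endpoint (9.1.2):** patients who received Yselty "at a dose of 200 mg for more than 6 months without concomitant prescriptions for ABT". There is no condition on the starting regimen.
- **Variable (9.3.6):** prescription of 200 mg "without concomitant ABT in defined time periods; Yes/No (see section 9.1.2". This too carries no condition on the starting regimen.
- **Analysis (9.7.3.4):** "Number and percentage of patients with an initial treatment dose of 200 mg without ABT that are not treated with ABT after" at least 6, 9, 12, 15 and further months, while staying on 200 mg.

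The lists of regimens also differ.

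- **Exposure (9.3.4)** records four: "Dosing regimen (200 mg with ABT, 200 mg without ABT, 100 mg with ABT, 100 mg without ABT". It also records start and stop dates, reasons for regimen change, and reasons for interrupting or stopping ABT.
- **Table 1** names three: "dosing regimen (100 mg without ABT, 100 mg with ABT, or 200 mg with ABT".
- **The DXA-frequency display (9.7.3.4)** uses three: "stratified by dose (100mg/100mg + ABT/200mg + ABT".

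**The concern.** The endpoint and the analysis meant to deliver it define different groups. The analysis sentence fixes the group by its first regimen, so anyone who reaches 200 mg without ABT later is outside the count. The protocol itself foresees such changes, since 9.3.4 collects reasons both for changing regimen and for stopping ABT.

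The primary objective covers 200 mg with ABT and 100 mg with or without it. II.h is therefore the dedicated check on 200 mg without ABT. If the analysis follows 9.7.3.4 literally, the reported number of prolonged users can be too low, and the error can only make prescribing look more compliant.

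**Working it through.** The protocol gives no figure for this check, so there is none to reproduce. The main step is to apply both definitions to the possible histories.

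**Step 1. Who is counted.** Take patients who each spend well over six months on 200 mg without ABT.

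| History | Endpoint, 9.1.2 | Analysis, 9.7.3.4 |
|---|---|---|
| Starts on 200 mg without ABT and stays on it | counted | counted |
| Starts on 100 mg, moves to 200 mg without ABT | counted | not counted |
| Starts on 200 mg with ABT, later stops ABT | counted | not counted |

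Dropping the second and third rows cannot add patients, so the restriction leaves the number the same or lowers it. This holds for the number. The percentage is less clear: if it is taken over starters on 200 mg without ABT, its denominator also differs from that of an all-patient endpoint.

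**Step 2. Whether another planned output supplies the number.**

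- The transition table (9.7.3.4) compares the baseline regimen with the end-of-study regimen. It misses periods that begin and end in between, and gives no durations.
- The ABT interruption and discontinuation summaries give incidence and reasons, not months on 200 mg afterwards.
- Endpoint II.e gives time on each regimen and changes of regimen, not the number of patients past six months on this one.

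None gives the II.h count.

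**Step 3. Possible size (assumed inputs).** Let s be the prolonged users who started on 200 mg without ABT, and u those who reached it later. The endpoint counts s + u and the analysis counts s, so the share captured is s/(s + u). The protocol gives neither value. Per 1,000 patients, with s from 5 to 20 and u from 0 to 40:

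| s | u | Endpoint count | Analysis count | Captured |
|---|---|---|---|---|
| 5 | 0 | 5 | 5 | 5/5 = 100% |
| 10 | 10 | 20 | 10 | 10/20 = 50% |
| 10 | 20 | 30 | 10 | 10/30 = 33% |
| 10 | 40 | 50 | 10 | 10/50 = 20% |
| 20 | 40 | 60 | 20 | 20/60 = 33% |
| 5 | 40 | 45 | 5 | 5/45 = 11% |

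The table shows how the share depends on the split between routes. It is not an estimate.

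**Step 4. The cut.** 9.1.2 requires strictly more than six months; 9.7.3.4 starts at six months or more. The two differ only for a patient at exactly six months. There 9.7.3.4 is the more inclusive, so this small discrepancy runs the opposite way to the restriction.

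**Step 5. The regimen lists.** Four in 9.3.4, against three in Table 1 and three in the DXA display. The one missing each time is 200 mg without ABT.

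**The case against.** The strongest reply is that little is lost. Section 9.3.4 records all four regimens with dates and reasons for change, II.e describes switching, off-label use is listed under 9.7.3.5, and 9.1 leaves further detail on switching to the SAP. All of that stands. A reader might infer that later step-ups and ABT stops vanish from the study; they do not. They are missing only from this check.

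It is also fair that Table 1 is headed as an estimated schedule, names the regimens only in a parenthesis, and has a separate row for regimen changes. A reader might infer from it that 200 mg without ABT will not be captured. The document does not show that: the eCRF is not available, and 9.3.4 points the other way. The two places conflict and need reconciling, no more.

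The DXA strata match the regimens in the primary objective and are an additional display, so the overall DXA result does not depend on them. Section 7 gives a six-month limit for 200 mg without ABT, and the follow-up DXA windows begin at month 10. If that limit is observed, few such patients would appear there. Section 9.7.2 also allows stratification by regimen, to be specified in the SAP. What remains is that the display does not say where such patients go.

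Finally, a reader might infer that late entry is the usual route to this regimen. Section 7 describes 200 mg as used when needed and with ABT from the start, which makes late entry plausible. The same section, however, contemplates 200 mg without ABT for up to six months, so starting on it and overrunning is equally foreseeable. No frequencies are given for either.

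None of this reconciles the analysis sentence with its endpoint. That is a contradiction within the protocol, not a detail left for the SAP.

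**Conclusion.** The point holds as a mismatch of definitions. The 9.7.3.4 count covers a subset of the patients in endpoint II.h, so the restriction can only match or understate the endpoint number, and no other planned output supplies it.

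The amount is unknown. The illustrative range of 11% to 100% captured rests wholly on assumed values, and the shortfall is zero if nobody reaches the regimen late and stays on it past six months. A narrower figure such as 20–33% would need switching rates that the protocol does not contain.

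The differing cut and the three-against-four regimen lists are minor inconsistencies. The point concerns one part of one exploratory objective in a descriptive study and does not touch the primary endpoint or the study size. It should be fixed, but is not a bar to the study. It concerns reporting definitions only and takes no position on any dosing rule.

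**What to change.** - In 9.7.3.4, remove the condition on the initial treatment dose. Count every patient with a period on 200 mg without concomitant ABT that exceeds the stated duration, timed from the start of that period whatever the first regimen. State the denominator of the percentage. A split by route (initial regimen, step-up, ABT stopped) is optional.
- Use the same six-month cut in 9.1.2 and 9.7.3.4.
- Reconcile the regimen list in Table 1 with that in 9.3.4.
- State where patients on 200 mg without ABT appear in the dose-stratified DXA display.

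The cost is one rewritten sentence and a few words in Table 1 and in the description of the DXA display. No new data are needed, because 9.3.4 already collects regimen, dates and ABT stops. Data collection is planned to start in Q1/Q2 2026 and the SAP is listed as in progress, so the wording can be aligned before either is settled.

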  - Mean absolute and relative change in density (g/cm^2) and absolute value and relative change of BMD z-score and t-score from DXA scan at 12 months (for patients with multiple follow-up DXA scans as per routine clinical practice)

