### **9.2.6 Visits**

The physician documents an initial visit, follow-up visit(s), and a final visit for each patient in the electronic data capture (EDC) system. Follow-up visit(s) are documented as they occur per routine practice or physician's decision. The study protocol does not define exact referral dates for those visits. The expected schedule of the conduct of this study as per routine clinical practice is shown in Table 1. More than 1 visit per year can be recorded in the eCRF.

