BMD will be displayed as absolute and relative change in density ( $\text{g}/\text{cm}^2$ ) and absolute value and relative change of z-scores and t-scores over time by means of summary statistics; e.g., DXA scans performed at baseline (if available) vs. timepoint 1 – 1st year (+/-6 months) after treatment initiation, timepoint 1 – 1st year (+/-6 months) after treatment initiation vs. DXA scans performed at timepoint 2 – 2nd year (+/-6 months), where the measurements are at least 6 months apart. This is continued in the same way for further years if the sample size is at least 5 patients. Changes are only analysed if e.g., the machine types, the location of the scan and other criteria that allow comparability are consistent. A subgroup analysis of t-scores for the subgroup of postmenopausal patients and of z-scores in the subgroup of premenopausal patients will be conducted, if sample size allows. Additionally, patients who experienced BMD decrease during the study but continued to be observed in the study, regardless of the reason for which Yselty® treatment was discontinued, will be investigated as a separate subgroup. This subgroup analysis will include the presentation of both absolute value and relative change of z-scores and t-scores after discontinuation. If the sample size permits, this subgroup will be stratified based on whether alternative treatments administered after discontinuation may also lead to a decrease in BMD (refer to “previous systemic treatments” in section 9.3.3).

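### Objective II.j averages BMD changes over scan pairs 6 to 24 months apart without allowing for elapsed time, so differences in scan timing can look like differences in bone loss

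*Protocol*

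**What the plan says.** Protocol section 9.1.2 defines the II.j endpoints as means of change, beginning "Mean absolute and relative change in density". One set is measured from baseline and the other "from DXA scan at 12 months". Both also cover z-scores and t-scores.

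Section 9.7.3.4 sets out the analysis. BMD is shown "over time by means of summary statistics". The comparisons, given as examples, are baseline against year 1 and then year 1 against year 2: "6 months) after treatment initiation vs. DXA scans performed at timepoint 2". Each yearly time point carries a tolerance of 6 months either side. Pairs qualify "where the measurements are at least 6 months apart". The scheme continues for later years if at least 5 patients are available. Pairs must agree on machine type, scan location and other unnamed comparability criteria. The scan interval is not among the criteria named.

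The protocol does not control when scans happen. Section 9.2.6 says: "The study protocol does not define exact referral dates for those visits". It expects routine visits about every 12 months. For a different purpose, objective II.h counts patients who "received at least 1 DXA scan between 10 months until 14 months".

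**The concern.** Bone loss builds up with time on treatment, so a change in BMD can be read only together with the time over which it arose. Under the written rule, a pair 6 months apart and a pair 24 months apart enter the same mean with equal weight. The mean then reflects both how fast bone is lost and when scans happened to be taken.

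This matters more here than in a trial with fixed visits:

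- Section 9.1 says visit frequency may depend on the country, and section 9.9 says DXA reimbursement may help or hinder scanning by country.
- Section 9.7.2 plans stratification by country and dosing regimen where numbers allow.
- Section 9.1 plans to set BMD results for patients on add-back therapy from the start beside published real-world data for another product. That comparison needs a known interval.
- Section 7 gives sustained loss at a slow rate as the reason for the study.

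**Working it through.** The protocol gives no precision or expected value for the II.j analysis, so there is no figure to reproduce. Table 2 concerns the primary endpoint only.

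**Inputs from section 9.7.3.4.** Year 1 is 12 ± 6, or months 6 to 18. Year 2 is 24 ± 6, or months 18 to 30. The minimum gap is 6 months and there is no maximum.

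**Range of gaps.**

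- Year 1 to year 2: the smallest possible gap is 18 − 18 = 0, raised to 6 by the minimum rule. The largest is 30 − 6 = 24. Admissible gaps are 6 to 24 months.
- Baseline to year 1: 6 − 0 = 6 to 18 − 0 = 18 months, if the baseline scan is at treatment start. No earliest date for a pre-treatment scan is stated, so the upper end could be longer.

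**Effect on one pair.** At a constant loss rate r per year, a pair with gap G months shows r × G/12.

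| Comparison | Gap (months) | Multiple of annual loss | At r = 1% | At r = 3% |
|---|---|---|---|---|
| Year 1 to year 2 | 6 to 24 | 0.5 to 2.0 | 0.5% to 2.0% | 1.5% to 6.0% |
| Baseline to year 1 | 6 to 18 | 0.5 to 1.5 | 0.5% to 1.5% | 1.5% to 4.5% |

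The protocol states no loss rate, so the rates are illustrations. The multiples do not depend on them.

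**Effect on the mean.** Assume scan dates are independent and uniform within each window. The year-1/year-2 gap is then triangular on 0 to 24 with its peak at 12.

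- Share of pairs failing the 6-month rule: ½ × (6/12)² = 12.5%.
- These short pairs contribute ∫₀⁶ g²/144 dg = 0.5 month to the overall mean of 12.
- Mean gap of the pairs kept: (12 − 0.5)/0.875 = 13.1 months.
- Simulation of 2,000,000 pairs agrees: mean 13.1, SD 4.1, 5th to 95th percentile 7.0 to 20.5 months.
- Ratio to one year: 13.1/12 = 1.09 to 1.10, or about 10% too much.

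The shift arises because the minimum gap removes short pairs while nothing removes long ones. Baseline/year-1 pairs have no such shift under the same assumption (mean 12.0, SD 3.5).

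**Effect on comparisons.** Take two strata with the same loss of 1% per year but mean gaps of 9 and 15 months. They show 1 × 9/12 = 0.75% and 1 × 15/12 = 1.25%. These gaps are chosen for illustration.

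**Small samples.** With 5 pairs, the lowest number at which later years are reported, the mean gap varies by about 1.96 × 4.1/√5 = 3.6 months around 13.1. Timing need not average out.

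**The case against.** The strongest reply has four parts.

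**The detail belongs in the SAP.** The pairing is introduced as an example, the comparability criteria are open-ended, and sections 9.7.1 and 9.7.3.5 leave calculated variables and further details to the SAP, which is not at hand. A SAP could add scaling. This stands in part. However, the windows, the minimum gap and the mean-change measure are already written in the protocol, and a SAP that simply followed them would carry the problem over.

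**The extremes are unlikely.** Visits are expected about yearly, so most gaps may lie near 12 months. This stands: the 6-to-24-month range is a limit, and even uniform timing moves the mean by only about 10%.

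**Scaling has costs.** Dividing a 6-month change by half a year doubles its measurement error, and section 9.9 already warns about DXA accuracy in routine practice. A mixed model is hardly workable with 5 patients. Narrower windows would discard scans that section 9.9 expects to be scarce. All of this stands and shapes the fix.

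**The endpoint is exploratory.** II.j is one of ten exploratory objectives in a descriptive study. This stands and limits the weight of the point.

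A reader might also infer more than the text supports:

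- *That the protocol presents these changes as annual rates.* It does not. It reports change between labelled time points.
- *That II.j contradicts II.h.* The 10-to-14-month window in II.h measures whether physicians perform the annual scan, a different purpose that can justify a different window. The later II.h periods are cumulative (for example, months 10 to 26), so they offer no ready-made window for year 2.
- *That a reference scan at 6 to 12 months breaches II.j.* A reference naturally precedes the long-term period, and II.j also allows baseline. The 12-month label is imprecise, not contradictory.
- *That month 18 leads to a scan being paired with itself.* The 6-month rule prevents that. Only a shared boundary point remains.

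**Conclusion.** The concern holds for exploratory objective II.j. As written, mean BMD change mixes loss with scan timing: gaps are 6 to 24 months between years 1 and 2, and about 6 to 18 months from baseline to year 1 if the baseline scan is at treatment start.

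The overall mean is affected modestly. It is about 10% above a one-year change for year-1/year-2 pairs under uniform, independent scan dates and constant loss, and less if scans cluster near yearly visits. The larger risk is in comparing countries, regimens or outside data whose scan timing differs. The size of that effect depends on timing differences that the protocol cannot predict.

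The primary endpoint, the proportion of patients with a z-score below −2, does not use this pairing and is unaffected. The point is a worthwhile, low-cost improvement and does not threaten the study's main result.

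**What to change.** Keep the planned windowed means as the main display, and add to section 9.7.3.4 or the SAP:

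1. For each comparison and stratum, the distribution of actual intervals between paired scans (number, mean, SD, median, quartiles, minimum, maximum).
2. Change in density (g/cm²) per year, using the actual elapsed time between scan dates. Where numbers allow, use instead a mixed model of density on actual time since first dose.
3. A rule that assigns a month-18 scan to one window only, and likewise at later boundaries.

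Do not annualise relative change in z- or t-scores, which is unstable when the starting value is near zero. Do not narrow the windows for the main display. Windows of 2 months either side would limit year-to-year gaps to 8 to 16 months (22 − 14 to 26 − 10), but at the price of losing scarce scans.

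The cost is some extra analysis. Scan dates and the first-dose date are already collected, so no further visits, scans or data are needed. The downside is that annualising assumes roughly linear change within the interval and magnifies measurement error for short gaps. The per-year figures should therefore stand beside the planned means, not replace them.
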